8.1. Efficacy Assessments

Not applicable.

8.2. Safety Assessments

Planned time points for all safety assessments are provided in the SoA (Section 1.3).

8.2.1. Physical Examinations

Complete physical examinations and symptom-directed physical examinations will be conducted at the visits specified in the SoA (Section 1.3). Symptom-directed physical examinations may

also be conducted at other visits, as determined by the investigator, if a participant presents with complaints. A complete physical examination will include, at a minimum, assessments of the

- cardiovascular
- respiratory
- gastrointestinal, and
- neurological systems.

Height and weight will also be measured and recorded as per SoA (Section 1.3).

8.2.2. Vital Signs

For each participant, vital sign measurements should be conducted according to the SoA (Section 1.3) and as clinically indicated.

Vital sign measurements should be obtained before collection of blood samples (applicable for study visits).

Blood pressure and PR should be measured after at least 5 minutes in a supine position.

Note: If white-coat hypertension is suspected at screening, the participant can be included in the trial if a repeated measurement (up to 2 additional assessments) shows values within the acceptable range.

If orthostatic measurements are required, participants should be supine for at least 5 minutes and stand for at least 2 minutes. If the participant feels unable to stand, only supine vital signs will be recorded.

Unscheduled orthostatic vital signs should be assessed, if possible, during any AE of dizziness or posture-induced symptoms. Additional vital signs may be measured during each study period if warranted.

Body temperature will be measured, as specified in the SoA (Section 1.3), and as clinically indicated.

8.2.3. Electrocardiograms

Single and triplicate 12-lead ECGs will be obtained as specified in the SoA (Section 1.3). Electrocardiograms must be recorded approximately within 30 minutes before collecting any blood samples (applicable for study visits). Participants must be supine for approximately 5 to 10 minutes before ECG collection and remain supine but awake during ECG collection.

Electrocardiograms may be obtained at additional times, when deemed clinically necessary. Collection of additional ECGs at a particular time point is allowed to ensure high-quality records.

Electrocardiograms will be interpreted by a qualified physician, the investigator, or qualified designee at the site as soon after the time of ECG collection as possible. Ideally, the participant should be present

- to determine whether the participant meets entry criteria at the relevant visit(s), and
- for immediate participant management, should any clinically relevant findings be identified.

The machine-read ECG intervals and HR may be used for data analysis and report writing purposes unless a cardiologist overread of the ECGs is conducted prior to completion of the final study report (in which case the overread data would be used).

Single electrocardiograms

Single ECGs will be collected at screening, at early termination, and follow-up on Days 29 and 43 according to the SoA (Section 1.3). Single ECGs may be obtained at additional times when deemed clinically necessary to assess participants' safety. All single ECGs recorded should be stored at the investigational site. Single ECGs will not be transmitted to a central laboratory.

Triplicate electrocardiograms

Triplicate 12-lead ECGs will be obtained as specified in the SoA (Section 1.3).

Collection of more ECG replicates than expected at a certain time point will be permitted to ensure high-quality records. At each time point at which triplicate ECGs are required, 3 individual ECG tracings should be obtained as closely as possible in succession, but no more than 2 minutes apart. The full set of triplicates should be completed in less than 4 minutes.

Scheduled and unscheduled digital ECGs will be electronically transmitted to a central ECG laboratory designated by the sponsor. The central ECG laboratory will perform a basic quality control check, for example, demographics and study details, then store the ECGs in a database. At a future time, the stored ECG data may be overread at the central ECG laboratory for further evaluation of machine-read measurements or to meet regulatory requirements.

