4.1. Overall Design

Study GZHF is a Phase 1, single-center, randomized, placebo-controlled, multiple dose, dose-escalation study in 4 planned cohorts of up to 14 healthy participants randomly assigned in each cohort.

This study will evaluate the safety, tolerability, and PK of 3 consecutive once-daily oral doses of LY3493269. In addition, the PD effects of LY3493269 on fasting glucose, insulin, triglycerides, and appetite will be explored following the 3 consecutive oral once-daily doses of LY3493269.

In each cohort, up to 14 participants may be randomly assigned to achieve 10 completers with 8 participants receiving LY3493269 and 2 participants assigned to receive placebo. Participants who are randomly assigned but not administered treatment prior to discontinuation may be replaced to ensure that the target number of participants complete the study.

This is an investigator- and participant-blind study; the sponsor is not blinded.

Study randomization shall occur after confirmation of eligibility.

The planned LY3493269 oral doses for this study range from 8 to 48 mg (Section 1.2), administered in the 4 planned "dose cohorts":

- Cohort 1: 8 mg LY3493269 (with 600 mg SNAC)
- Cohort 2: 24 mg LY3493269 (with 600 mg SNAC)
- Cohort 3: 48 mg LY3493269 (with 600 mg SNAC)
- Cohort 4: 24 mg LY3493269 (with 300 mg SNAC)

Cohorts 1 to 3 evaluate doses of LY3493269 from 8 to 48 mg, each dose in combination with 600 mg SNAC. Cohort 4 evaluates a 24-mg dose of LY3493269 with half the amount (300 mg) of SNAC. PK exposures from 24 mg LY3493269 administered with half the amount of SNAC (i.e. 300 mg SNAC in Cohort 4) are anticipated to be comparable to exposures from the 24-mg dose in Cohort 2, and not exceed exposures from the 48-mg dose in Cohort 3. Hence, Cohort 4 may be initiated at the same time as Cohort 3 if safety and tolerability data from Cohort 2 do not preclude dosing of 24 mg LY3493269 or higher doses.

The LY3493269 dose levels may be adjusted (for example, dose increments may be reduced, a dose level may be repeated, or a lower/intermediate dose may be administered) based on ongoing review of available safety, tolerability, PK, and PD data (Section 6.6). Any proposal to adjust doses from those planned and stated in the protocol, together with supporting data, will be reviewed by an independent SRP.

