9.6.6 Electrocardiogram

The ECG data will be obtained directly from the 12-lead ECG traces. These data include the PR, QT, QRS duration, RR and HR. In addition, QTcF will be calculated as follows:

$$QTcF = \frac{QT}{\sqrt[3]{\frac{60}{HR}}}$$

The ECG data will be summarized by treatment together with changes from baseline, where baseline is defined as the mean of the triplicate Day 1 -0.5 h, -0.25, and predose assessments. Figures of mean ECG data and mean changes from baseline will be presented by treatment. The frequency of participants with a maximum increase from baseline in QTcF interval will be summarized for each treatment according to the following categories: >30 ms and >60 ms. In addition, the frequency of participants with QTcF postdose values, according to the following categories: >450 ms, >480 ms and >500 ms, will be summarized by treatment.

Plasma PK Concentration versus delta and double delta ECG parameter analysis

A plasma LY3493269 concentration-ECG parameter analysis will be performed to assess the relationship between changes from baseline (mean of Day 1 -0.5 h, -0.25 h, and predose

triplicate assessments) in ECG parameters (QTc, PR interval, QRS duration, and HR) and plasma LY3493269 concentrations across all treatments. The change from baseline adjustment will be based on individual participant's Day 1 -0.5 h, -0.25 h, and predose values. Further details on how these will be calculated:

- Calculate the baseline ECG value for each participant, which is the mean of ECG parameter values of each individual participant over 3 predose time points at Day 1.
- Calculate the change from baseline at each timepoint for each individual participant.
- Calculate the mean ECG parameter value across all participants at baseline.
- For each participant subtract the mean ECG parameter value from their own individual observed ECG parameter value. This will be each participant's centered ECG parameter value.
- BLQ LY3493269 concentration data will be imputed to the lower limit of quantification/square root(2) for the purposes of the analysis.

The relationship between LY3493269 concentrations and ECG parameters will be explored graphically by plotting delta ECG parameter values against LY3493269 concentrations, including all post dosing timepoints.

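### The source of the ECG values stays open until the final report, and a central overread would leave the Day 29, Day 43 and early-termination changes from baseline mixing two reading methods

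*Protocol*

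**What the plan says.** Protocol 8.2.3 sets the default and the exception in one sentence. Machine-read intervals and heart rate serve by default. The exception is a cardiologist's reading, when an "overread of the ECGs is conducted prior to completion of the final study report (in which case the overread data would be used"). The triplicate part of the same section adds: "At a future time, the stored ECG data may be overread at the central ECG laboratory", and gives the possible reasons as "for further evaluation of machine-read measurements or to meet regulatory requirements". Neither document gives a trigger, a decision date relative to unblinding or database lock, or a requirement that the reader be blind to treatment.

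On who knows what, Protocol 4.1 states: "This is an investigator- and participant-blind study; the sponsor is not blinded". Protocol 9.5 and SAP 10 confirm that the sponsor team is unblinded at the data reviews, and Protocol 6.6.1 lists ECGs up to Day 8 among the data reviewed before each escalation.

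On which tracings can be overread, the screening, Day 29, Day 43 and early-termination ECGs are single tracings kept at the site: "Single ECGs will not be transmitted to a central laboratory". The triplicates do go to the central laboratory.

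SAP 9.6.6 says only that the data come from the 12-lead traces and never mentions an overread. Its "baseline is defined as the mean of the triplicate Day 1 -0.5 h, -0.25, and predose assessments", so the baseline consists entirely of tracings that a central overread would cover. It plans summaries of change from baseline by treatment, counts of participants whose maximum QTcF increase exceeds 30 and 60 ms, and a concentration-ECG model. It does not exclude Days 29 and 43 from any of these. SAP 11 reports no changes from the protocol analyses.

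**The concern.** There are two separate problems.

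The first is timing. Whether the machine-read data are replaced can be decided at any point before the report is finished, by a team that may already have seen the machine-read results by arm. If that decision depended on the results, the QTcF estimates and outlier counts would be biased.

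The second needs no assumption about anyone's behaviour, only that the central overread takes place. The triplicates would then be overread and the single ECGs would not. A change from baseline at Day 29, Day 43 or early termination would be a machine-read value minus an overread baseline, and would contain the difference between the two methods as well as any change in the participant. The outlier counts use each participant's maximum increase, so one such value can move a participant into a category. With 8 active participants per cohort, one participant is 1/8 = 12.5 percentage points.

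**Working it through.** The plan gives no figure on this point to reproduce. Three checks follow.

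**1. How much of the schedule a central overread misses.** From the Schedule of Activities (Protocol 1.3), triplicates are taken at 7 time points on Day 1, 4 on Day 2, 7 on Day 3, and once on each of Days 4, 5, 6, 8 and 15: 7 + 4 + 7 + 5 = 23 time points, or 69 tracings. Three of the Day 1 time points precede the first dose and form the baseline (9 tracings), which leaves 20. Adding the single ECGs on Days 29 and 43 gives 22 scheduled time points after the first dose. The share outside a central overread is 2/22 = 9%, plus any early-termination visit.

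**2. Bias from a results-dependent decision to overread.** Let s be the standard error of the machine-read estimate and of the overread estimate, and ρ their correlation. Suppose an overread is commissioned only when the machine-read estimate lies above its expectation, and then replaces it. The retained machine-read half contributes −s·φ(0) and the overread half contributes +ρ·s·φ(0), so

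bias = −(1 − ρ)·s·φ(0), with φ(0) = 1/√(2π) = 0.399.

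The documents give neither s nor ρ. Assuming s = 3 to 5 ms and ρ = 0.5 to 0.9:

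- s = 3, ρ = 0.9: 0.1 × 3 × 0.399 = 0.12 ms downward
- s = 5, ρ = 0.5: 0.5 × 5 × 0.399 = 1.00 ms downward

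A simulation of the same rule agrees with the formula: −0.79 ms against −0.80 ms at s = 4, ρ = 0.5.

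**3. Effect of mixing methods.** If machine values exceed overread values by b ms on average, a machine-read value minus an overread baseline is shifted by +b in full. In a placebo-corrected difference the shift is b − b = 0 if b is the same in both arms.

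To illustrate the >30 ms count, assume independent tracings with a single-tracing SD of 10 ms and no drug effect. The SD of one single ECG minus the mean of 9 baseline tracings is 10 × √(1 + 1/9) = 10.54 ms. The chance of exceeding 30 ms at one visit is p = 1 − Φ((30 − b)/10.54), and at either of two visits 1 − (1 − p)².

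| Assumed offset b (ms) | Chance at Day 29 or 43 | Expected excess among 8 active participants |
|---|---|---|
| 0 | 0.4% | – |
| 5 | 1.8% | 8 × (0.0176 − 0.0044) = 0.1 |
| 10 | 5.7% | 8 × (0.0569 − 0.0044) = 0.4 |
| 15 | 14.9% | 8 × (0.1487 − 0.0044) = 1.2 |

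The two visits share a baseline. Allowing for that gives 1.8%, 5.6% and 14.6% for the last three rows, which changes nothing of substance. An offset in the other direction would hide true increases.

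**The case against.** A reader might infer that the sponsor can see both readings and keep the more favourable one. That would be worth s·√((1 − ρ)/π), or 0.54 to 1.99 ms on the same assumed inputs. The text does not allow it. The rule runs one way: an overread completed before the report must be used. The only discretion is whether to commission one, when its result is still unknown. No section says who decides, and one of the stated reasons, a regulatory requirement, need not depend on the results. Nothing in the documents suggests intent. Protocol 9.5 also mentions a possible separate unblinding plan, which is not available here.

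A reader might also infer that the follow-up changes are certain to be wrong. They are affected only if an overread is done, and only if it is confined to the central laboratory. Protocol 8.2.3 does not say where the cardiologist would read, so a site overread of the single tracings is not excluded, although the central route is the only one described. The TFL shells, which define the displays, are not available either.

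Finally, the main QTcF inference is largely protected. Pooled placebo is its own column in the tables (SAP 6), so a common offset would be visible there. The time and day effects in the concentration-ECG model (SAP 9.6.6) would absorb most of it. QTcF is a supporting safety analysis, since the primary endpoint is TEAEs and the secondary endpoints are AUC and Cmax.

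All of this limits the size of the problem. It does not supply the missing statement of source, and it does not protect the within-arm changes or the category counts.

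**Conclusion.** The point holds in a limited form. The documents permit the decision to replace the ECG data to be taken after unblinded machine-read results have been seen, and the SAP does not close that gap. The resulting bias would be modest: about 0.1 to 1.0 ms downward if commissioning depended on a high machine-read estimate, under the assumed standard error of 3 to 5 ms and correlation of 0.5 to 0.9.

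The mixing of methods is conditional on a central overread and confined to 2 of 22 scheduled time points after the first dose, plus early termination. Where it occurs, the offset passes in full into the within-arm change from baseline and the >30 and >60 ms counts, and largely cancels in placebo-corrected contrasts. Its size is unknown. The SD of 10 ms and the offsets of 5 to 15 ms are illustrations, and only the 15 ms case adds more than one expected participant per active cohort.

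The documents give no reason to insist that machine-read values be primary. Either reading can serve, provided that it is named in time.

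**What to change.** Amend Protocol 8.2.3 and SAP 9.6.6 in two places.

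1. Compute every change from baseline with the same reading method at both ends. If the triplicates are overread, the Day 29, Day 43 and early-termination singles are compared with the machine-read Day 1 baseline.
2. State, before the first unblinded ECG review, whether machine-read or overread values are the analysis source. Report any other reading done later beside it as a sensitivity analysis, covering all triplicates and made by a reader blind to treatment.

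Both are wording changes and need no new data. The first has no downside. The second has a small one: a later, unplanned overread that corrected machine errors would appear next to the headline values and would not replace them.

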8.2.4. Clinical Safety Laboratory Assessments

See Appendix 2 (Section 10.2) for the list of clinical laboratory tests to be performed and to the SoA (Section 1.3) for the timing and frequency.

The investigator must review the laboratory report, document this review, and record any clinically relevant changes occurring during the study in the AE section of the CRF. The laboratory reports must be filed with the source documents. Clinically significant abnormal laboratory findings are those which are not associated with the underlying disease, unless judged by the investigator to be more severe than expected for the participant's condition.

All laboratory tests with values considered clinically significantly abnormal during participation in the study or within 28 days after the last dose of study intervention should be repeated until the values return to normal or approximately baseline or are no longer considered clinically significant by the investigator or medical monitor.

- If such values do not return to normal/approximately baseline within a period of time
 judged reasonable by the investigator, the etiology should be identified and the sponsor
 notified.
- All protocol-required laboratory assessments, as defined in Appendix 2 (Section 10.2), must be conducted in accordance with the laboratory manual and the SoA (Section 1.3).
- If laboratory values from non-protocol specified laboratory assessments performed at the institution's local laboratory require a change in participant management or are considered clinically significant by the investigator (e.g., SAE or AE or dose modification), then the results must be recorded in the CRF.

8.2.5. Safety Monitoring

The Lilly clinical pharmacologist or CRP will monitor safety data throughout the course of the study.

Lilly will review SAEs within time frames mandated by company procedures. The Lilly clinical pharmacologist or CRP will periodically review the following data:

- trends in safety data
- laboratory analytes
- serious and non-SAEs including monitoring of GI events, hypoglycemia, and hypersensitivity reactions and reported and adjudicated pancreatitis

When appropriate, the Lilly clinical pharmacologist or CRP will consult with the functionally independent Global Patient Safety therapeutic area physician or clinical research scientist.

8.2.5.1. Hepatic Safety

Close hepatic monitoring

Laboratory tests (see Appendix 6;Section 10.6), including ALT, AST, ALP, TBL, creatine kinase, and direct bilirubin, should be repeated, with addition of gamma-glutamyl transferase, within 48 to 72 hours to confirm the abnormality and to determine if it is increasing or decreasing, if 1 or more of these conditions occur:

If a participant with baseline results of	develops the following elevations:		
ALT or AST <1.5 × ULN	ALT or AST ≥3 × ULN		
ALP <1.5 × ULN	ALP ≥2 × ULN		
TBL <1.5 × ULN	TBL ≥2 × ULN (except for participants with Gilbert's syndrome)		
ALT or AST ≥1.5 × ULN	ALT or AST ≥2 × baseline		
ALP≥1.5 × ULN	ALP ≥2 × baseline		
TBL ≥1.5 × ULN	TBL ≥2 × baseline (except for participants with Gilbert's syndrome)		

Abbreviations: ALP = alkaline phosphatase; ALT = alanine aminotransferase; AST = aspartate aminotransferase; TBL = total bilirubin level; ULN = upper limit of normal.

If the abnormality persists or worsens, clinical and laboratory monitoring, and evaluation for possible causes of abnormal liver test results should be initiated by the investigator in consultation with the Lilly-designated medical monitor. At a minimum, this evaluation should include physical examination and a thorough medical history, including symptoms, recent illnesses (for example, heart failure, systemic infection, hypotension, or seizures), recent travel, history of concomitant medications (including over the counter), herbal and dietary supplements, and history of alcohol drinking and other substance abuse.

Initially, monitoring of symptoms and hepatic biochemical tests should be done at a frequency of 1 to 3 times weekly, based on the participant's clinical condition and hepatic biochemical tests. Subsequently, the frequency of monitoring may be lowered to once every 1 to 2 weeks, if the participant's clinical condition and laboratory results stabilize. Monitoring of ALT, AST, ALP, and TBL should continue until levels normalize or return to approximate baseline levels.

Comprehensive hepatic evaluation

A comprehensive evaluation should be performed to search for possible causes of liver injury if 1 or more of these conditions occur:

If a participant with baseline results of	develops the following elevation:
ALT or AST <1.5 × ULN	ALT or AST ≥3 × ULN with hepatic signs/symptoms ^a , or ALT or AST ≥5 × ULN
ALP <1.5 × ULN	ALP ≥3 × ULN
TBL <1.5 × ULN	TBL ≥2 × ULN (except for participants with Gilbert's syndrome)
ALT or AST ≥1.5 × ULN	ALT or AST ≥2 × baseline with hepatic signs/symptoms ^a , or ALT or AST ≥3 × baseline
ALP≥1.5 × ULN	ALP ≥2 × baseline
TBL ≥1.5 × ULN	TBL ≥1.5 × baseline (except for participants with Gilbert's syndrome)

Abbreviations: ALP = alkaline phosphatase; ALT = alanine aminotransferase; AST = aspartate aminotransferase; TBL = total bilirubin level; ULN = upper limit of normal.

At a minimum, this evaluation should include physical examination and a thorough medical history, as outlined earlier, as well as tests for prothrombin time-INR; tests for viral hepatitis A, B, C, or E; tests for autoimmune hepatitis; and an abdominal imaging study (for example, ultrasound or CT scan).

Based on the participant's history and initial results, further testing should be considered in consultation with the Lilly-designated medical monitor, including tests for

- hepatitis D virus
- cytomegalovirus
- Epstein-Barr virus
- acetaminophen levels
- acetaminophen protein adducts
- urine toxicology screen
- Wilson's disease
- blood alcohol levels
- · urinary ethyl glucuronide, and
- blood phosphatidylethanol.

Based on the circumstances and the investigator's assessment of the participant's clinical condition, the investigator should consider referring the participant for a

- hepatologist or gastroenterologist consultation
- magnetic resonance cholangiopancreatography
- endoscopic retrograde cholangiopancreatography
- cardiac echocardiogram, or a
- liver biopsy.

^a Hepatic signs/symptoms are severe fatigue, nausea, vomiting, right upper quadrant abdominal pain, fever, rash, and/or eosinophilia >5%.

Additional hepatic data collection (hepatic safety CRF) in study participants who have abnormal liver test results during the study

Additional hepatic safety data collection in hepatic safety CRFs should be performed in study participants who meet 1 or more of the following 5 conditions:

- 1. Elevation of serum ALT to \geq 5 × ULN on 2 or more consecutive blood tests (if baseline ALT <1.5 × ULN)
 - a. In participants with baseline ALT \geq 1.5 × ULN, the threshold is ALT \geq 3 × baseline on 2 or more consecutive tests
- 2. Elevation of TBL to $\ge 2 \times$ ULN (if baseline TBL <1.5 \times ULN) (except for cases of known Gilbert's syndrome)
 - a. In participants with baseline TBL \geq 1.5 × ULN, the threshold should be TBL >2 × baseline
- 3. Elevation of serum ALP to $\ge 2 \times$ ULN on 2 or more consecutive blood tests (if baseline ALP <1.5 ×ULN)
 - a. In participants with baseline ALP \geq 1.5 × ULN, the threshold is ALP \geq 2 × baseline on 2 or more consecutive blood tests
- 4. Hepatic event considered to be an SAE
- 5. Discontinuation of study drug due to a hepatic event

Note: the interval between the 2 consecutive blood tests should be at least 2 days.

